The INSPIRE-ASP Trial (INtelligent Stewardship Prompts to Improve Realtime Empiric Antibiotic Selection for Patients) for Skin and Soft Tissue (SST) Infections Protocol

> NCT:05423756 6/24/2020

Brief Overview

The INSPIRE-ASP Trial (INtelligent Stewardship Prompts to Improve Real-time Empiric Antibiotic Selection for Patients) for Skin and Soft Tissue (SST) Infections is a cluster-randomized trial of 92 hospital randomized units (102 individual hospitals) to improve physicians' choice of antibiotics for patients hospitalized with SST infections by reducing the unnecessary use of extended-spectrum antibiotics. This trial provides prescribers in half the hospitals with prescribing advice based on the probability that a patient is infected with antibiotic resistant bacteria. Provision of unnecessary extended-spectrum antibiotics carry risks, and the goal of this trial is to limit their use to situations in which the patient is likely to require them, while maintaining excellent patient outcomes.

We hypothesize that providing clinicians with individual patient risk estimates for antibiotic-resistant infections will reduce the overuse of empiric extended-spectrum antibiotics among patients hospitalized for SST infections. To do this, we will use patient information in the electronic health record plus local hospital laboratory data on antibiotic resistance in SST cultures to develop an automated smart tool that provides the likelihood that a patient needs extended-spectrum antibiotics. 102 hospitals were randomized into 92 hospital were randomized to either routine care orto the intervention arm receiving the INSPIRE Stewardship Bundle units, into either routine care (46 hospital units) or to the intervention arm (46 hospital units) receiving the INSPIRE Stewardship Bundle which includes CPOE smart prompts, clinician feedback reports, and activities to support CPOE adoption (e.g., education and modifications of CPOE workflows as needed). In half of hospitals, physicians will be prompted to use standard-spectrum antibiotics when the risk of an antibiotic-resistant infection is low. This 12-month intervention will evaluate approximately 61,000 patients with SST infections.

Protocol Summary

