This protocol provides detailed instructions for the conduct of the INSPIRE-ASP Trial (INtelligent Stewardship Prompts to Improve Real-time Empiric Antibiotic Selection for Patients) for Skin and Soft Tissue (SST) Infections. This trial is a 92 hospital unit (102 individual hospitals), 61,000 patient, cluster-randomized trial to improve physicians' choice of antibiotics for hospitalized patients by reducing the unnecessary use of broad-spectrum antibiotics while maintaining excellent patient outcomes. This trial will be conducted in the HCA Healthcare system, which provides 5% of acute care services in the United States.

Hospitals will be recruited through usual HCA Healthcare communication channels and randomized into a two-arm trial involving routine care or routine care plus a stewardship bundle that includes real-time personalized risk calculator for whether a patient with SST infection is infected with an antibiotic-resistant pathogen warranting extended-spectrum antibiotic therapy. This protocol details eligibility criteria for participation, factors accounted for in 1:1 hospital randomization, notification of randomization assignment, and provision of the two arms with arm-specific toolkit information and coaching calls. It also details the process by which centralized IRB approval and reliance agreements will be obtained.

This trial evaluates a quality improvement antibiotic stewardship strategy, the INSPIRE Stewardship Bundle, that includes (1) computerized physician order entry (CPOE) decision support alert that provides physicians with patient-specific risk estimates for having a (ABD) infection due to a multidrug-resistant organism (MDRO) and recommends standard spectrum antibiotics for low risk patients in the first 3 days of hospitalization; (2) clinician feedback reports, and (3) activities to support CPOE adoption (including education and alignment of CPOE workflows). As such, study implementation will be performed through the local infrastructure provided by hospital antibiotic stewardship program leaders who serve as study champions. Participating hospitals in both arms will approve the arm-specific study protocol through usual hospital committees. The routine care arm will participate in regular coaching calls to ensure best practice for national standards of stewardship are taught and encouraged. This arm will also launch a trial-specific modification to the existing antibiotic indication screen.

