Several activities are detailed for the INSPIRE Stewardship Bundle arm. These include pre-launch activities such as participation in coaching calls and an on-site training visit, as well as procedures to locally install corporate MediTech software for the CPOE personalized risk calculator for SST antibiotic indications, including any modifications needed to align the CPOE workflow to support the INSPIRE prompts (e.g., order-based exclusion of ICU patients, order set changes). In addition, the sites receiving the INSPIRE Stewardship Bundle will receive educational materials, participate in monthly coaching calls and every other month check in

calls, and receive clinician audit reports to feedback to physicians and hospital leadership about protocol adherence.

As a pragmatic trial, all data will be obtained from the HCA Healthcare centralized clinical data warehouse. Local site champions will not need to collect any outcome data or variables for description or adjustment. This protocol describes how data will be obtained through a data use agreement between HCA Healthcare and the Harvard. Data and programmer analysts will access and analyze data on the HCA Healthcare server behind the HCA Healthcare firewall, thus ensuring maximum data protections.

In summary, the INSPIRE Trial for Skin and Soft Tissue (SST) Infections is a randomized trial of 92 hospital units (102 individual hospitals) and approximately 61,000 infected patients to improve physicians' choice of antibiotics for patients hospitalized with SST infection by reducing the unnecessary use of extended-spectrum antibiotics. This trial protocol provides the road map for the conduct of the trial to determine if a personalized real-time risk calculator plus audit and feedback can improve judicious use of antibiotics in hospitalized patients.

B. Background Information and Scientific Rationale

B.1. Background Information

National Call for Antibiotic Stewardship in an Era of Antibiotic Resistance

Inappropriate use of extended-spectrum antibiotics is a major driver of the 2 million antibiotic-resistant infections in the U.S. each year. 1,2 Nearly 40% of inpatient antibiotics are inappropriate or unnecessary. 3,4 Unfortunately, rising antibiotic resistance has fueled rather than curbed extended-spectrum antibiotic use, with prescribers using extended-spectrum agents for the possibility of resistance, thus leading to a detrimental cycle that urgently needs attention. 5

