- Provide information on how to install the computerized physician order entry (CPOE) risk calculator into your local Meditech system
- Detail the toolkit that you will receive for intervention guidance
- Describe the feedback and audit reports

D. Study Design and Population

Title: The INSPIRE-ASP Trial (INtelligent Stewardship Prompts to Improve Real-time Empiric

Antibiotic Selection for Patients) for Skin and Soft Tissue (SST) Infections.

Study Design: Cluster-randomized trial

Participant: 102 Hospitals affiliated with HCA Healthcare randomized into 92 units. Hospitals with

shared antibiotic stewardship teams (physicians or pharmacists) are randomized together as a single hospital unit. Inclusion criteria includes affiliation with HCA Healthcare and use of Meditech (for standardized build of CPOE prompts for the INSPIRE Stewardship Bundle arm). Any qualifying facility wishing to participate will be permitted to enroll even if in excess of calculated study sample size to accommodate HCA Healthcare facility or division-level antibiotic stewardship goals. Exclusion criteria include care of <100 SST infection patients per year, and implementation or planned implementation of a new antibiotic stewardship intervention directly conflicting with the

trial in the baseline or intervention period.

Population: The analytic cohort will be patients with SST. Inclusion criteria include adults ≥18 years

old admitted to a general medical or surgical floor (non-ICU) of a participating HCA Healthcare hospital with a diagnosis of SST infection. In addition, patients must receive a systemic antibiotic in the first 3 days of hospitalization (empiric period). Exclusion criteria will include age <18 years old and ICU admission on either hospital day 1 or 2. Hospitals that do not use Meditech are excluded from participation, as are those who

use/will use Meditech Expanse or Patient Keeper for order entry.

Number of Sites: 92 HCA Healthcare hospital hospital units (102 individual hospitals)

Study Duration: 5-month phase-in period (does not contribute to analysis) and 12-month intervention

period

Subject Duration: Eligible hospital admission

Schematic of Study Design:

Figure 1: Two Study Arms of the INSPIRE-ASP Trial

Current HCA Healthcare Policy

Clinicians determine empiric antibiotic therapy for patients admitted with SST infection

Arm 1: Routine Care (N = 46 hospital units)

- Routine prescribing practice for SST infection

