Power assessment proceeded as follows, using a Monte Carlo approach.²⁵ We used available data to define a baseline period of 1/1/2019-12/31/2019. In a bootstrap procedure, individuals were selected with replacement from within each hospital, once to represent baseline data and separately to represent "intervention period" data. Hospitals were then "randomized" to intervention or control according to multiple parameters, including number of admissions with SST infection and ES-DOT. We then modified the outcomes for the bootstrapped individuals in the "intervention" period in the "intervention" arm to reflect the effect of the intervention.²⁹

We assessed power to identify an overall 12.5% relative reduction in ES-DOT. This effect was implemented by reducing the relative empiric days of therapy for each admission which was exposed to the CPOE prompt. The amount of reduction was a uniform random variate between 0.75 and 1. For example, if the bootstrapped patient initially received 8 ES-DOT and was assigned to have a have a 12.5% reduction, then that admission intervention ES-DOT would be reduced to 7 days. The reduction of ES-DOT was selected with a lower bound determined by the investigators as the minimal effect achieved that would be clinically meaningful. Using this method, we have ≥99.9% (99.6-99.9%) power to detect this effect.

Since adoption of the intervention will be heavily influenced by the ability to demonstrate safety, our study size was based on the power to detect non-inferiority for safety outcomes. We used methods similar to the above to calculate the power to identify at least a one day increase in length-of-stay for 12.5% of patients who had hospitalizations less than 14 days and found the power was 68.9% (CI 65.9-71.8%), where non-inferiority is defined as a hazard ratio no smaller than 0.98. For days to ICU transfer, we estimated the power to detect a 2% increase in transfers to the ICU on hospital day 3 through 14 to be >99.9% (CI 99.6-99.9%), where non-inferiority is defined as having a hazard ratio no greater than 1.1 (fewer days to ICU results in a hazard ratio above 1).

For completeness, we note that there are other pre-specified outcomes intended for exploratory analysis in secondary papers for the INSPIRE ABD trial in Table 4 below.

Table 4: Secondary Manuscripts - Other Pre-Specified Outcomes

Secondary Manuscripts (other pre-spe-	cified secondary exploratory analyses for later manuscripts)

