The primary trial analysis will use an as-randomized unadjusted model with two-tailed significance set at alpha = 0.05. The secondary outcome will be assessed using an as-randomized unadjusted model with alpha = 0.05.

Subsequent analyses of the primary and secondary outcome will include both as-treated and adjusted models. Adjusted models will account for individual characteristics such as age, gender, comorbidities, and prior history of MDROs as well as hospital characteristics such as hospital antibiotic resistance. We will also account for seasonality. All adjusters will be determined a priori. These analyses will be reported as point estimates with confidence intervals and without p-values. The reason for including these analyses is to provide additional information related to the trial outcomes for readers to assess the effects of potential confounders. The reason to not include them in a formal multiple comparisons adjustment is because these analyses are non-independent evaluations relative to the as-randomized unadjusted analyses.

Safety Outcomes

Safety outcomes are required because a reduction in ES-DOT might be achieved only by incorrectly withholding ES antibiotics when they were necessary. Each safety outcome will be

evaluated for non-inferiority using an as-randomized unadjusted analysis with a one-tailed significance set at alpha = 0.05. For length of stay, the non-inferiority margin is a hazard ratio of 0.98. For days to ICU transfer, the non-inferiority margin is a hazard ratio of 1.1 (fewer days to ICU results in a hazard ratio above 1). Analyses planned for these assessments are proportional hazards models with random effects for each time period, hospital, and admission. These models are sometimes called frailty or shared frailty models. Because these are safety outcomes, we do not intend to make adjustments for multiple comparisons in testing them, further increasing conservatism. As above, it may not be possible to include multiple admissions.

All analyses will be performed using current versions of SAS/STAT and/or R packages Ime4 and coxme, unless better packages become available in the meantime.

Further Planned Analyses

We note that there are other pre-specified outcomes intended for exploratory analysis in secondary papers for the INSPIRE SST trial in Table 5 below.

Table 5: Secondary Manuscripts - Other Pre-Specified Outcomes

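### The confirmatory models omit the factors used to balance hospital randomisation, so standard errors are conservative to the extent that those factors predict the 2019-to-2023 change

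*Protocol*

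**What the plan says.** The Protocol Summary states that the protocol details the "factors accounted for in 1:1 hospital randomization". Section E.1 (Randomization) lists none. The only factors named are in the Power Size/Sample Size Calculations section, where simulated hospitals are allocated on multiple parameters, including "number of admissions with SST infection and ES-DOT".

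The confirmatory analyses do not carry these factors. SAP, Primary Statistical Analysis: "The primary trial analysis will use an as-randomized unadjusted model with two-tailed significance set at alpha = 0.05". The secondary outcome is handled the same way. Under SAP, Safety Outcomes, length of stay and ICU transfer are each "evaluated for non-inferiority using an as-randomized unadjusted analysis"; the only further terms described are random effects at period, hospital and admission level.

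Two other provisions bear on this. Both documents base the main evaluation of every outcome on a difference in differences between periods and arms. The primary Poisson model has a hospital intercept (b0h) and a hospital-by-period effect (b1h), so baseline-period ES-DOT is part of the data being modelled. Adjusted models are planned for the primary and secondary outcomes only, as supportive estimates without p-values. Their example adjusters do not include SST volume, baseline ES-DOT or a randomisation stratum. No reason is given for leaving the design factors out.

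**The concern.** When allocation is balanced on a factor that predicts the outcome, the between-arm variation due to that factor is removed from the estimate. A model that omits the factor still counts this variation as error. The estimate stays unbiased, but its reported standard error is too large, the test runs below its nominal level, and intervals are wider than the design warrants.

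This matters most for the safety outcomes. The protocol says the study size was set by power for non-inferiority on safety, and the stated power for length of stay is 68.9% against a hazard-ratio margin of 0.98. In a non-inferiority test, an inflated standard error makes it harder to show safety. What has to be settled is how much of this mechanism survives a difference-in-differences analysis.

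**Working it through.** **Inputs from the documents.** 92 units, 46 per arm. About 61,000 patients in the intervention period, so 61,000/92 ≈ 663 per unit. Target effect 12.5%, so ln(0.875) = −0.1335. Stated power at least 99.9% (ES-DOT) and 68.9% (length of stay). 91% of stays last 14 days or less. **Assumed, because the documents give no variances:** squared coefficient of variation of admission-level ES-DOT (CV²) 1 to 4; SD of b1h 0 to 0.2; share of change variance explained by the factors (R²) 5% to 30%.

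**1. The plan's own primary power.** The bootstrap draws both periods from the same hospital's 2019 data, so it contains no real hospital-by-period change: SD(b1h) = 0. Then SE = √[(SD(b1h)² + 2·CV²/663)·(2/46)]. With CV² = 2 this is √[(4/663)(2/46)] = 0.0162, and power exceeds 99.99% for CV² from 1 to 4. This agrees with the stated figure but is not an exact reproduction, since CV² is assumed.

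**2. Does difference in differences remove the loss?** Simulation of 92 units, pair-matched on volume and baseline ES-DOT; 4,000 runs per setting, CV² = 2, SD of baseline log rate 0.3, two-sided 5%, no true effect:

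| Analysis | SD(b1h) | Share of b1h variance explained | Model SE | True SE | Type I error |
|---|---|---|---|---|---|
| Post-period only, unadjusted | 0 | none | 0.064 | 0.045 | 0.6% |
| Difference in differences, unadjusted | 0 | none | 0.0162 | 0.0164 | 5.4% |
| Difference in differences, unadjusted | 0.2 | none | 0.0446 | 0.0453 | 5.3% |
| Difference in differences, unadjusted | 0.2 | 30% | 0.0447 | 0.0391 | 2.6% |
| Same, with factor-by-period terms | 0.2 | 30% | 0.0385 | 0.0392 | 5.5% |

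The textbook loss appears in the post-period comparison. In the planned type of model it disappears unless a factor predicts the change.

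**3. When would a factor predict the change?** Suppose the unit-level outcome has equal variance σ² in both periods and between-period correlation ρ. Then Var(change) = 2σ²(1−ρ) and Cov(change, baseline) = −σ²(1−ρ), so baseline explains R² = (1−ρ)/2 of the change. Values of ρ of 0.9, 0.8, 0.6 and 0.4 give R² of 5%, 10%, 20% and 30%. This is regression to the mean.

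**4. Size.** The SE ratio is 1/√(1−R²), and the actual one-sided size is P(Z > 1.645/√(1−R²)):

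| R² | SE too large by | Critical value used | Actual size |
|---|---|---|---|
| 5% | 3% | 1.688 | 4.6% |
| 10% | 5% | 1.734 | 4.1% |
| 20% | 12% | 1.839 | 3.3% |
| 30% | 20% | 1.966 | 2.5% |

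A unit-level simulation pair-matched on baseline agrees: unadjusted size 4.6%, 4.1%, 3.6% and 2.3%, and 4.9% to 5.4% after adjustment.

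**5. Consequence for primary power.** With SD(b1h) = 0, adjustment changes nothing. With SD(b1h) = 0.1 and 9% of its variance explained, power is 99.95% either way. With SD(b1h) = 0.2, power moves from 85% to 87% (9% explained) or from 87% to 93% (30% explained). If the factors explain nothing, adjusting costs almost nothing: 83.3% against 83.1%.

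**6. Length of stay.** Taking a true hazard ratio of 1, a power of 68.9% at one-sided 5% implies SE = −ln(0.98)/(1.645 + 0.493) = 0.0202/2.138 = 0.0094. Events are 61,000 × 0.91 = 55,510. Without clustering, SE is √(4/55,510) = 0.0085 for the intervention period alone (power 76.9%) and √(8/55,510) = 0.0120 for a difference in differences (power 51.5%). Neither matches 68.9%. On the first basis all between-hospital variance is at most 1 − (0.0085/0.0094)² ≈ 19% of the total (unrounded SEs); on the second, nothing is left for it.

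**The case against.** The strongest reply is that all outcomes are evaluated by difference in differences, so a factor's stable effect cancels, and baseline ES-DOT is already in the primary model. No passage shows that SST volume or any other factor predicts the change from 2019 to 2023. This stands, and it makes the loss conditional. It does not remove it. The power simulation cannot show that the change is unrelated to the factors, because it has no real change in it. The actual periods lie either side of a pandemic that the protocol says severely affected operations and case mix, and the model includes b1h to allow for hospital-level change.

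A reader might infer that adjustment would raise length-of-stay power markedly, for example to Φ(2.138/√0.8 − 1.645) = 77% if 20% of the variance were explained. The documents do not support this. The 68.9% came from methods similar to the primary simulation, which already balanced hospitals and resampled both periods from 2019 data, so hospital factors could not explain the change. The 77.2% also exceeds the 76.9% obtained with no clustering at all.

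Three smaller points are fair. Conservatism on safety is protective, and the protocol asks for a conservative assessment; but the size of this conservatism is unplanned and unknown. The SAP already expects difficulty fitting patient-level and repeat-admission effects, so extra terms are not entirely free. Finally, the named factors come from the simulated allocation; those actually used are not listed.

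**Conclusion.** The omission is real: hospitals are allocated with factors accounted for, and no confirmatory model has a term for them. The result is a conditional loss of precision, not bias and not an inflated error rate. If the factors explain 5% to 20% of the variance of the hospital-level change, the standard error is about 3% to 12% too large and a one-sided 5% test runs at about 4.6% to 3.3%. If they explain none of it, nothing is lost. The range rests on an assumed R², and on the actual factors resembling those in the power simulation.

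A reader might also infer that the primary analysis is underpowered as a result. At the stated power of at least 99.9% no material loss is shown. A visible gain requires assumed hospital-by-period variation (SD(b1h) around 0.2) that the documents do not report. For length of stay the direction of any gain is clear but its size cannot be given. This is an inexpensive improvement that should be made, not a failure of validity.

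**What to change.** List in Protocol section E.1, or in the SAP, the unit-level factors actually used to balance the randomisation. State in the SAP that the as-randomised primary, secondary, length-of-stay and ICU-transfer models include those factors (or the stratum or pair) and their interaction with period. The interaction is essential, because main effects alone cancel in a difference in differences. Keep the fully unadjusted model as a sensitivity analysis. The same terms would help most in the protocol's separate intervention-period comparison by arm, where omitting them costs most; there the factors enter as main effects.

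The SAP is dated 29 March 2024, after the intervention period ended, so the change must be fixed and dated before any arm-level result is seen. The cost is a few degrees of freedom out of 92 units, a sentence or two in the SAP and slightly more model-fitting work. The factors are already in hand because they were used to randomise.
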